#### 9.3.2 Dose Escalation

Subjects enrolled into the phase 1b portion will enroll at dosing level 1 with three patients per dosing level (3+3 design). A cycle will be 21-days. Based on toxicity

and activity seen during the phase lb portion, additional dose levels and/or alternate 28 day cycle may be explored through an amendment. The carfilzomib will be given intravenously weekly on days 1 and 8. The romidepsin will be given intravenously on days 1 and 8. The lenalidomide will be given as a once a day oral drug given on days 1-14. It is preferred that romidepsin be administered prior to carfilzomib.

TABLE 1: Phase I Dose Escalation			
Dose	Romidepsin	Lenalidomide	Carfilzomib
Level			(mg/m²)
-1	8 mg/m 	10 mg	20
1	8 mg/m 	15 mg	36
2	8 mg/m 	15 mg	45
3	10 mg/m 	20 mg	45
4	10 mg/m 	20mg	56
		J	

If all three patients complete one cycle of therapy without a DLT at the respective

- dose level then the subsequent dose level can be accrued.

  A DLT is defined in cycle 1 of the phase I portion as:

   Non-hematologic toxicity of grade ≥3 (attributed to study drugs with the exception of alopecia, nausea, or grade ≥3 vomiting not responsive to antiemetics)
  - Hematologic grade 4 toxicity (attributed to study drugs) defined as grade 4 thrombocytopenia of any duration; grade 4 neutropenia lasting more than 5 days; or grade 4 anemia unexplained by the underlying disease
  - Grade ≥3 thrombocytopenia with clinically significant bleeding
  - Febrile neutropenia of any duration (ANC <1.0K/ µL with fever 38.5°C)
  - Inability to receive day 1 of cycle 2 due to continued drug-related toxicity including Grade ≥ 2 toxicity that does not resolve to Grade ≤ 1 by the start of the next cycle.
  - Grade 3 thrombocytopenia or neutropenia (attributed to study drug) within cycle 1 that results in a) ≥ 4 day delay in any romidepsin or carfilzomib dose or b) missing greater than 4 days of lenalidomide. (This criteria only applies to the **phase lb portion** and does not apply to the phase Ila stopping rules).

After the MTD is determined by either DLT or accrual of six patients without DLT at dose level 4 in the first cycle accrual to the phase Ib portion will be considered closed. The MTD from the phase lb study will be used for the phase lla portion.

Of note, only patients who complete ≥80% of the doses of carfilzomib, romidepsin and lenalidomide during the first cycle will be evaluable for MTD. Patients who do

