not meet this criteria for minimum drug exposure and do not have a dose limiting toxicity will be replaced for determination of MTD.

The treatment plan is described below for the **phase lb portion**:

- Romidepsin/Lenalidomide/Carfilzomib: Romidepsin IVPB over 4 hours on days 1 and 8
- Carfilzomib IVPB administered over approximately 30 minutes on days 1 and 8\*\*
- Lenalidomide PO q days 1-14

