#### 9.5 **Dose Continuation, Modification and Interruption**

Subjects will be evaluated for AEs at each visit with the NCI CTCAE v4.0 used as a guide for the grading of severity. DLTs as defined will be tabulated in cycle 1 of phase Ib and cycles 1-4 of the phase Ila portion of the study. The toxicity decision rule for the Ila portion is described in Section 14.0. The sections below describe dose reduction steps, instructions for initiation of a new cycle of therapy and dose modifications during a cycle of therapy. Of note, if patient's experiences a greater than 10% change in body weight, dose of romidepsin should be adjusted accordingly. Doses do not need to be adjusted for less than 10% changes in body weight.

# 9.5.1 Instructions for Dose Modifications or Interruption During Phase 1 Cycle 1

There will be no dose reductions in cycle 1 phase 1. Inability to meet treatment criteria will result in holding the dose.

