# 9.5.2 Instructions for Dose Modifications or Interruption During Phase 1 Cycle 2 and beyond and phase 2 all cycles

Dose delay and dose reduction rulesare as follows and in the table below. The following dose modification criteria are applicable to adverse events related to study drugs:

- In the event of dose reduction due to toxicity all agents will be reduced as per Table 2, 3, 4. If an agent is already at its lowest dose per tables 2,3,4 then the other agents will be reduced. If the lowest doses are not tolerated the subject will be removed from the study.
- For treatment interruptions during a cycle, the 21-day schedule of each cycle will continue to be followed. Missed doses of lenalidomide, carfilzomib and romidepsin are not made up. For treatment interruptions that delay the scheduled start of a new cycle, when toxicity has resolved as required to allow the start of a new cycle, the restart day of therapy becomes Day 1 of the next cycle.
- If a patient is at the lowest dose level and deriving benefit from therapy, they may continue on protocol therapy despite ≥ grade 3 hematologic toxicity or non-clinically significant non-hematologic toxicity after discussion with the MSK principal investigator. A delay of planned study therapy of greater than 21 days with result in removal from study.

TABLE 2: Lenalidomide Dose Modification Steps		
Current Lenalidomide Dose	One Level Dose Reduction	
20 mg daily on Days 1-14 every 21 days	15 mg daily on Days 1-14 every 21 days	
15 mg daily on Days 1-14 every 21 days	10 mg daily on Days 1-14 every 21 days	
10 mg daily on Days 1-14 every 21 days	5 mg daily on Days 1-14 every 21 days	

TABLE 3: Romidepsin Dose Modification Steps		
Current Romidepsin Dose	One Level Dose Reduction	
10 mg/m  daily on Days 1,8	8 mg/m² daily on Days 1,8	
8 mg/m² daily on Days 1,8	5 mg/m² daily on Days 1,8	
5 mg/m² daily on Days 1,8	5 mg/m² daily on Days 1	
Carfilzomib Dose Modification Steps		
Current Carfilzomib Dose	One Level Dose Reduction	
56 mg/m 	45 mg/m 	
45 mg/m 	36 mg/m 	
36mg/m 	20 mg/m 	

TABLE 4: Dose Modifications for Lenalidomide, Carfilzomib and Romidepsin for Phase 1 cycle 2 and beyond/ Phase 2 all cycles		
NCI CTC Toxicity Grade	Dose Modification Instructions	
, , ,	(also see Instructions for Initiation of a New Cycle above)	

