NCI CTC Toxicity Grade	(also see Instructions for Initiation of a New Cycle above)			
Neuropathy	
 
If Grade 3, hold (interrupt) romidepsin, lenalidomide and carfilzomib dose. Follow at least weekly.
 
			
Grade 3	• If the toxicity resolves to ≤ grade 1 prior to Day 14 of the current cycle, restart lenalidomide, romidepsin and carfilzomib at next lower dose level and continue through the scheduled Day 14 of the current cycle. Otherwise, omit for remainder of cycle and reduce the dose of lenalidomide, romidepsin and carfilzomib by 1 dose level at the start of the next cycle. Omitted doses are not made up.			
Grade 4	
 
If Grade 4, discontinue lenalidomide and carfilzomib. Remove patient from study. Responding patients may continue on romidepsin off of study.
 
			
Venous thrombosis/embolism ≥ Grade 3	
 
Hold (interrupt) carfilzomib, lenalidomide and romidepsin. Start therapeutic anticoagulation, if appropriate.
 
Restart carfilzomib, lenalidomide and romidepsin at investigator"s discretion after discussion with the MSK PI (reduce 1 dose level of each drug).
 
See Anticoagulation Consideration
 
			
Hyperthyroidism or hypothyroidism	
 
Omit lenalidomide, carfilzomib, and romidepsin for remainder of cy evaluate etiology, and initiate appropriate therapy.
 
See Instructions for Initiation of a new cycle and reduce the dose lenalidomide by 1 dose level.
 
			
Other related non-hematologic toxicity ≥ Grade 3 including grade 3:  • Pulmonary hypertension • Congestive heart failure • Myocardial ischemia • Decreased ventricular function • Hepatic toxicity • Pulmonary complications • Renal Failure	
 
Hold (interrupt) lenalidomide, carfilzomib romidepsin dose. Follow at least weekly.
 
If the toxicity resolves to ≤ grade 2 prior to Day 14 of the current cycle, restart lenalidomide, carfilzomib and romidepsin at one dose level lower and continue through the scheduled Day 21 of the current cycle. Otherwise, omit for remainder of cycle. Omitted doses are not made up. Otherwise, omit for remainder of cycle and reduce the dose of lenalidomide, carfilzomib and romidepsin by 1 dose level at the start of the next cycle.
 
For patients with ≥ grade 3 nausea or vomiting, dose reductions are only required for patients who had persistent ≥grade 3 vomiting despite use of oral and/or IV antiemetics.
 
			

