#### 14.0 BIOSTATISTICS

The standard dose-escalation scheme for this study is as follows. Patients will be accrued to the study in cohorts of 3. For any given dose an initial cohort of 3 patients will be treated at that dose. The dose level will be escalated if none of the 3 patients exhibits any DLT in the first cycle as defined above. If a DLT is observed in one patient, an additional cohort of 3 patients will be treated at that dose. The dose will be escalated if none of the additional 3 patients exhibits any DLT. Dose-escalation stops and the previous dose will be considered the MTD if 2 or more patients have a DLT. If the previous dose level has been administered to only 3 patients, an additional 3 patients will be enrolled to confirm the result. For this design the probability of escalation is as follows:

True toxicity rate	5%	10%	15%	20%	25%	30%	40%	50%
Probability of escalation	0.97	0.91	0.81	0.71	0.60	0.49	0.31	0.17

Dose escalation will start with dose level 1. A dose level -1 is also added to the design to ensure a minimum level of toxicity (we expect this dose level will be quite tolerable for patients based on the phase I data of romidepsin and lenalidomide). The maximum number of patients needed for this dose escalation design is 30. We estimate accrual to be 2 patients per month. Patients with measurable disease treated at MTD in the phase Ib will be analyzed in phase Ila to further characterize the toxicity of carfilzomib, romidepsin and lenalidomide in combination at the MTD determined by phase Ib. In phase IIa, we plan to enroll patients so that the total number of patients enrolled in each disease type cohort (B-cell lymphoma and T-cell lymphoma) will include 10 patients at the MTD. We estimate accrual to be 1 patient per month in each disease type cohort. To consecutively monitor the safety primary endpoint in the phase IIa portion, we will employ a sequential probability stopping rule for the predefined DLT in the phase lb portion of cycles 1-4. This stopping rule specifies that the study will be terminated if DLT occur in: ≥3/first 6; ≥6/first 12; or if more than 10 patients when the last (20th) evaluable patient has completed the trial have any DLT. This rule has the following stopping probability:

True toxicity rate	5%	10%	15%	20%	25%	30%	35%	40%	50%
Stopping prob.	0.002	0.016	0.049	0.104	0.184	0.289	0.413	0.548	0.797
C									

e

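### The DLT definition is inverted for vomiting: it exempts grade ≥3 vomiting that antiemetics fail to control and counts grade ≥3 vomiting that they do control

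*Combined protocol and SAP*

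**What the plan says.** Section 9.3.2 (Dose Escalation) lists the DLT criteria. The first is attributed non-hematologic toxicity of grade ≥3, "with the exception of alopecia, nausea, or grade ≥3 vomiting not responsive to antiemetics". Alopecia, nausea and the vomiting phrase all sit in one parenthesis governed by one exception.

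Table 4 in Section 9.5.2 sets dose modifications for phase Ib from cycle 2 and for all phase IIa cycles. For grade ≥3 nausea or vomiting, "dose reductions are only required for patients who had persistent ≥grade 3 vomiting despite use of oral and/or IV antiemetics". When a reduction is made, "In the event of dose reduction due to toxicity all agents will be reduced". Section 9.5.3 adds that doses should not be reduced for vomiting that has not had aggressive antiemetic support.

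The DLT definition is used in both phases. Section 9.5 states that "DLTs as defined will be tabulated in cycle 1 of phase Ib and cycles 1-4" of phase IIa. Section 14.0 says of phase IIa that "we will employ a sequential probability stopping rule for the predefined DLT". Section 9.3.2 marks only one criterion as phase Ib-only, the grade 3 cytopenia-delay one, which "does not apply to the phase Ila stopping rules".

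**The concern.** The clause is back to front. Vomiting that resists antiemetics is the kind that limits dosing, and vomiting that antiemetics settle is the kind normally excused. As written, the bullet excuses the first and counts the second.

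DLT decides the MTD in phase Ib and is the event monitored by the phase IIa stopping rule, so the error sits in the primary safety endpoint. Vomiting is an expected toxicity: Section 11.0 lists it as likely for all three drugs. The trial is multicenter. A site reading the clause literally and a site reading it by presumed intent would score the same event differently.

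In phase Ib there is a further route. Patients who fall below 80% of planned doses in cycle 1 and "do not have a dose limiting toxicity will be replaced for determination of MTD". A patient whose exposure was cut by refractory vomiting, with no other DLT, would be replaced rather than counted.

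**Working it through.** **Classification.** The two rules side by side, for attributed grade ≥3 vomiting with no other DLT criterion met:

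| Event | DLT under the 9.3.2 bullet | Dose reduction under Table 4 |
|---|---|---|
| Not controlled by antiemetics | No (inside the exception) | Yes |
| Controlled by antiemetics | Yes (general rule applies) | No |

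Sections 9.5 and 14.0 refer back to the definition without restating it, so the bullet reaches phase IIa cycles 1–4 unchanged.

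**The exemption is partial.** Refractory vomiting still counts under a separate criterion, "Inability to receive day 1 of cycle 2 due to continued drug-related toxicity", which includes grade ≥2 toxicity not resolved to grade ≤1. It also counts if another attributed grade ≥3 toxicity accompanies it. It does not count if it resolves before cycle 2. In phase IIa, the cycle 2 day 1 criterion as worded does not reach vomiting that first arises in cycles 2–4.

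**Reproducing the plan's figures (Section 14.0).**

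- 3+3 escalation: P = (1−p)³ + 3p(1−p)²·(1−p)³. At p = 5, 10, 15, 20, 25, 30, 40 and 50% this gives 0.973, 0.906, 0.814, 0.709, 0.600, 0.494, 0.309 and 0.172. All match the printed table to two decimals.
- Phase IIa stopping: exact binomial with looks at 6, 12 and 20 patients, stopping at ≥3, ≥6 and ≥10. At 30% the three looks contribute 0.2557 + 0.0262 + 0.0068 = 0.289. The printed values are reproduced throughout, including 0.184 at 25%, 0.289 at 30% and 0.413 at 35%. The text words the last look as more than 10 of 20, which gives 0.183, 0.283 and 0.400. Both versions are carried below.

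Neither printed table changes when the clause is corrected, because each is a function of whatever DLT rate is supplied. What changes is the rate that enters.

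**Illustration of size (assumed inputs).** Let the correctly counted DLT rate be 30%. Let r be the percentage points of refractory-only vomiting wrongly left out, and s the points of responsive-only vomiting wrongly counted. The counted rate is 30% − r + s. The documents supply neither r nor s nor the 30%.

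Phase IIa stopping probability, with ≥10 of 20 at the last look (more than 10 in parentheses):

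| | s = 0 | s = 2 | s = 5 |
|---|---|---|---|
| r = 0 | 0.289 (0.283) | 0.336 (0.328) | 0.413 (0.400) |
| r = 2 | 0.244 (0.241) | 0.289 (0.283) | 0.361 (0.352) |
| r = 5 | 0.184 (0.183) | 0.223 (0.220) | 0.289 (0.283) |

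Equal shares cancel in the stopping probability, although individual patients are still misclassified. A net error of 1 point either way gives 0.266 to 0.312 with ≥10 of 20 at the last look.

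**The case against.** Table 4 governs dosing, not DLT scoring, and it does not apply in phase Ib cycle 1, where the MTD was set and no reductions are made. Nor is it inconsistent in itself that an event forces a reduction without being a DLT. Under Table 4, grade 3 cytopenia that does not recover within 4 days requires a reduction, yet the cytopenia-delay criterion is expressly kept out of the phase IIa rule. Both points stand. The conflict is one of clinical logic between two rules, not two versions of one definition.

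The intended meaning can also be inferred. The bullet is already limited to grade ≥3, so repeating that grade before vomiting alone suggests a qualifier meant to bring refractory vomiting back in. This supports calling it a slip. It does not repair the text, because an operative endpoint definition should not depend on each site silently reversing it.

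Only half of the inversion weakens safety. Counting controlled vomiting makes escalation less likely and stopping more likely. That is true, and it is why no net direction is claimed.

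Finally, practical exposure is limited. The MTD is already fixed at dose level 1, prophylactic antiemetics precede both infusions (Section 9.4), holds and reductions apply in every phase IIa cycle, and all adverse events are recorded. No misclassified patient is shown, and the stopping-probability range rests on invented rates. All of this stands and bears on the weight of the point. It does not make the clause correct.

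**Conclusion.** The concern holds. The literal text reverses the treatment of grade ≥3 vomiting in the definition behind the primary safety endpoint, and no other section corrects it. That conclusion rests on the wording alone.

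The effect on trial decisions cannot be derived from the documents. The range of 0.184 to 0.413 shows only what errors of up to 5 points each would do at an assumed 30% rate; its ends are the two one-sided extremes, and 5 points is one patient in 20. Exposure is confined to the DLT tally. With the MTD already set, the phase IIa count is the part most exposed. The correction should be made, but there is no evidence that a past decision was wrong.

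**What to change.** Reword the exception in Section 9.3.2 to: *alopecia, nausea, or grade ≥3 vomiting that responds to antiemetics*. Refractory grade ≥3 vomiting then counts as a DLT, in line with the logic of Table 4 and Section 9.5.3.

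Check every recorded grade ≥3 vomiting event against the corrected wording, including events in phase Ib patients who were replaced for low exposure. Report whether any phase Ib DLT count or phase IIa stopping count changes. If none does, say so.

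The cost is a few words in one bullet by amendment, plus a review of events that the Adverse Event Reporting section already requires to be recorded, in about 30 expected patients. No new procedures or data are needed.

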#### 10.1 EVALUATION DURING TREATMENT/INTERVENTION

# 10.2 Assessments During Treatment: Phase 1, cycle 1 and cycle 2; phase 2, cycle 1

A patient may receive treatment on day 1 or day 8 of the first cycle if he or she meets the following parameters on the day of treatment:

- ANC is ≥ 1.0 K/µL Platelet count is ≥ 80 K/µL or within 10 K/µL of baseline for cycle 1 day 1 and platelet count ≥ 50 K/µL for cycle 1 day 8. (In the Phase II portion, if thrombocytopenia is due to bone marrow involvement platelet count must be ≥ 50 K/µL),
- Serum creatinine concentration ≤ 2.0 × ULN or ≤ baseline Serum potassium must be confirmed to be greater than or equal to the lower limit of normal for the testing laboratory, or corrected to those levels.
  - Supplements must be given to patients whose potassi um and/or magnesium are below the aforementioned range.
    - Magnesium supplementation: If levels are below normal range, but within 0.5 units of the lower limit of normal, patients can receive at least 2gm magnesium IV and proceed to treatment without re-checking labs. Patients can be treated if magnesium levels are above normal range.
- Potassium supplementation: If levels are below normal range, but within 0.3 units of the lower limit of normal, patients can receive at least 20mEq potassium and proceed to treatment without re-checking labs. Any drug-related rash or neuropathy that may have occurred has resolved to ≤ grade 1 severity
- Any other drug-related adverse events that may have occurred have resolved to ≤ grade 2 severity.

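### The phase Ib 80%-dose evaluability rule and the missed-dose DLT criterion do not meet, so a patient can leave the MTD decision because of drug toxicity; the effect on the declared MTD is unknown

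*Combined protocol and SAP*

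**What the plan says.** The rules are in Section 9.3.2 (Dose Escalation) of the combined protocol.

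- **Planned cycle 1 doses.** "The lenalidomide will be given as a once a day oral drug given on days 1-14"; "The romidepsin will be given intravenously on days 1 and 8"; "The carfilzomib will be given intravenously weekly on days 1 and 8". That is 14 + 2 + 2 = 18 doses.
- **Evaluability.** Evaluable for the MTD are "only patients who complete ≥80% of the doses of carfilzomib, romidepsin" and lenalidomide in the first cycle. The text does not say whether the 80% applies to each drug or to all doses together.
- **Replacement.** Anyone below the threshold without a DLT is replaced ("not meet this criteria for minimum drug exposure and do not have a dose limiting toxicity will be replaced for determination of MTD"). No exception is made for doses missed because of drug toxicity.
- **Missed-dose DLT.** A drug-related grade 3 thrombocytopenia or neutropenia is a DLT if it delays an infusion by 4 days or more, or leads to "missing greater than 4 days of lenalidomide". No other toxicity has a missed-dose criterion in cycle 1.
- **Other DLTs that matter here.** Non-hematologic toxicity from grade 3, with listed exceptions, and drug-related toxicity that still prevents day 1 of cycle 2.

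In phase Ib cycle 1 a dose is held, not reduced, when treatment criteria are not met (Section 9.5.1, instructions for Phase 1 Cycle 1). For day 1 or day 8 of the first cycle those criteria include: "Any drug-related rash or neuropathy that may have occurred has resolved to ≤ grade 1 severity" (Section 10.2). Section 14.0 escalates on 0 of 3 DLTs, or on 1 of 3 followed by 0 of 3, and stops at two or more. The phase IIa treatment plan states that dose level 1 has been determined to be the MTD.

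**The concern.** The MTD is part of the primary endpoint and sets the phase IIa dose. It is decided on three to six evaluable patients per level, so one patient's classification can separate 1 in 6 from 2 in 6. If a patient misses doses because of study drug, falls below 80% and has no listed DLT, that patient is taken out of the count and another is enrolled. Being counted then depends on the outcome that the design is meant to measure. The question is whether the DLT list closes this route, and if not, how far the escalation decision could move.

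**Working it through.** **1. The plan's own figure.** With DLT probability p, the Section 14.0 rule gives

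P(escalate) = (1−p)³ + 3p(1−p)² × (1−p)³.

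At p = 5, 10, 15, 20, 25, 30, 40 and 50% this is 0.973, 0.906, 0.814, 0.709, 0.600, 0.494, 0.309 and 0.172. All eight agree with the protocol's table (0.97, 0.91, 0.81, 0.71, 0.60, 0.49, 0.31, 0.17).

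**2. Where the 80% line falls against the DLT line.** Inputs are the 14, 2 and 2 planned doses. In the first four rows all infusions are assumed given.

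| Missed in cycle 1 | Per drug | Pooled over 18 | Missed-dose DLT if due to grade 3 cytopenia? |
|---|---|---|---|
| 2 lenalidomide days | 12/14 = 85.7% | 16/18 = 88.9% | No |
| 3 lenalidomide days | 11/14 = 78.6% | 15/18 = 83.3% | No |
| 4 lenalidomide days | 10/14 = 71.4% | 14/18 = 77.8% | No |
| 5 lenalidomide days | 9/14 = 64.3% | 13/18 = 72.2% | Yes |
| One infusion of one drug | 1/2 = 50% | 17/18 = 94.4% | Yes, if an omission counts as a delay of 4 days or more |
| Both Day 8 infusions | 1/2 = 50% for each | 16/18 = 88.9% | As above |

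Four lost lenalidomide days are below 80% on both readings and do not reach the missed-dose criterion. If no other DLT criterion is met, the patient is replaced. Three lost days fall in the gap only on the per-drug reading. On the pooled reading, combinations can also fall in it: both Day 8 infusions plus 2 lenalidomide days leave 14/18 = 77.8%.

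**3. Infusions lost to other toxicity.** Grade 2 rash or neuropathy bars the Day 8 dose under Section 10.2 but is below the non-hematologic DLT grade. If the dose is lost and the toxicity clears before cycle 2, there is no DLT. On the per-drug reading the patient has 50% of that drug and is replaced.

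**4. What replacement can do to escalation.** Let p be the listed-DLT rate and q the rate of patients who fall below 80% through drug toxicity without a listed DLT. The documents give neither, so both are assumed. The DLT rate entering the rule is p/(1−q) if these patients are replaced, p+q if they count as DLTs, and p if they count as evaluable without a DLT.

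For p = q = 15%, the rates are 0.15/0.85 = 17.6%, 30% and 15%. Over a wider range:

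| p | q | Replaced | Counted as DLT | Counted as evaluable, no DLT |
|---|---|---|---|---|
| 10% | 5% | 0.90 | 0.81 | 0.91 |
| 10% | 20% | 0.86 | 0.49 | 0.91 |
| 15% | 15% | 0.76 | 0.49 | 0.81 |
| 20% | 5% | 0.69 | 0.60 | 0.71 |
| 20% | 20% | 0.60 | 0.31 | 0.71 |

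Replacement lies between the two alternatives in every row. It makes escalation easier than counting these patients as DLTs and harder than counting them as free of DLT.

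**The case against.** The strongest case against has five parts.

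- **The 80% may be pooled.** Then 3 lost lenalidomide days, one lost infusion, or both Day 8 infusions all leave the patient evaluable. Appendix G tolerates a 3-day cycle 1 infusion delay for a recovering grade 3 cytopenia. That fits the pooled reading better if lenalidomide is held on the same days. This stands: only the 4-day case is free of the ambiguity.
- **Lost infusions are partly covered.** A delay of 4 days or more from grade 3 cytopenia is already a DLT, as is toxicity that still prevents cycle 2. A held Day 8 dose may also be given late: Section 10.3 speaks of delay, and the rule against making up doses is headed for phase 1 cycle 2 onward and phase 2. Section 10.3 also accepts non-hematologic toxicity up to grade 2 unless otherwise indicated. So the rash and neuropathy example needs Section 10.2 to govern and the dose to be lost. Creatinine and transaminases are weak examples. Section 10.3 sets no creatinine limit for Day 8, and a transaminase result from the previous 7 days can suffice.
- **The direction is open.** A reader might infer that replacement flatters the MTD. That follows only if the replaced patients should have been DLTs, and the protocol's definition does not make them so. Against counting them as evaluable without a DLT, replacement raises the rate (15% to 17.6%) and is the more cautious choice.
- **Replacement is limited and later safeguards exist.** It applies only to determining the MTD. Section 4.2 keeps phase Ib patients treated at the MTD with measurable disease in the toxicity endpoints, and phase IIa monitors DLTs over cycles 1-4. This helps, but Section 9.3.2 excludes the grade 3 cytopenia missed-dose criterion from the phase IIa stopping rules.
- **Future levels.** A reader might infer that further levels would follow the same 80% rule. Section 9.3.2 says only that they may be explored by amendment.

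What none of this removes is the 4-day gap, the undefined basis of the 80%, and replacement without regard to cause.

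**Conclusion.** The gap is real but narrow. A drug-related grade 3 cytopenia costing exactly 4 lenalidomide days, with no other DLT criterion met, is neither a DLT nor evaluable whether 80% is per drug or pooled. If it is per drug, the gap also covers 3 lost lenalidomide days and a Day 8 infusion lost to a non-DLT toxicity that clears before cycle 2. Exclusion from the MTD decision can therefore depend on drug toxicity.

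The documents do not show that the declared MTD is wrong or biased towards safety. They give no count of replaced patients, which could be zero. The illustration of 0.76 against 0.49 or 0.81 rests on assumed rates of 15% and 15%; with p = 10% and q = 5% the spread is only 0.90 against 0.81 or 0.91. The point matters because a reader cannot judge the dose level 1 claim without knowing who was replaced and why.

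**What to change.** 1. When reporting the MTD, show for each dose level all patients treated, those replaced, and the reason for their missed doses.
2. Give the DLT count with patients replaced for drug-related toxicity counted (a) as DLTs and (b) as evaluable without a DLT. State whether dose level 1 still has at most 1 DLT in 6 under both. Adding patients back can take the denominator above six, so also show the first six treated in order of entry.
3. State whether 80% is per drug or pooled over all cycle 1 doses.
4. Before any further dose level is opened by amendment, reconcile the 80% rule with the DLT list so that replacement does not depend on drug-related toxicity. State how patients below 80% through such toxicity count, and how an omitted infusion counts under the delay criterion. Merely keeping these patients without saying how they count would make them non-DLT by default and escalation easier (0.81 against 0.76 in the illustration). The clinical content of the DLT definition is for the sponsor to settle.

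The cost is one table from data already held, and a few sentences if levels are added. The downside is that the DLT rate at the MTD may look less favourable.
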